8.1. Change from Baseline in PRO Measures

For the PRO measures detailed in the subsections below, change from baseline analysis will be performed.

Summary statistics will be generated for each PRO measure for total patients and for patients by their TR03 core study treatment at Baseline, each Treatment Period study visit, the Washout and Safety Follow-up visit and LOV and for change from baseline in each PRO measure at each Treatment Period study visit, the Washout and Safety Follow-up visit and LOV.

Means and change from baseline means for each PRO with a continuous response will be presented in bar charts for all patients by study visit.

Values from all PRO measures will be presented in data listings.

8.1.1. Change from Baseline in Worst Itch Intensity NRS

The NRS is a patient-reported outcome instrument, designed to quantify the intensity of worst itching experienced during a 24-hour period. The scale is a set of boxes, one for each number, from 0 (no itching) to 10 (worst possible itching). The NRS is a widely used instrument recommended by International Forum for the Study of Itch (IFSI) for quantifying itch intensity as well as a useful instrument for grouping patients into categories of itch intensity described as mild, moderate or severe ([Stander et al 2013](#)). The itch NRS has been investigated in patients with chronic pruritus of a variety of origins and has a high reliability and concurrent validity was found ([Phan et al 2012](#)). The patient is to check the number that best reflects the worst itching during the prior 24 hours.

Summaries and bar charts of the worst itch intensity NRS scores will be presented as detailed in Section [8.1](#).

Worst itch intensity NRS values will be presented in a data listing.

8.1.2. Change from Baseline in Average Itch Intensity NRS

In addition to worst itch intensity, the patient is also to rate average itch intensity during the prior 24 hours.

Summaries and bar charts of the average itch intensity NRS scores will be presented as detailed in Section [8.1](#).

Average itch intensity NRS values will be presented in a data listing.

8.1.3. Change from Baseline in the VRS

The VRS scale to be used in this study has three dimensions, each dimension is coded with graduated adjectives (from 0 = none; to 5 = very severe) for the skin sensations of itchy, burning and stinging. Patients will be asked to record the VRS value: “How is your skin sensation today?”

Summaries of each of the three skin sensations will be presented as detailed in Section [8.1](#). In addition, for each of the three skin sensations, patients’ change between baseline and LOV will be summarized using frequencies and percentages for the following categories: 4 grades better, 3 grades better, 2 grades better, 1 grade better, no change (VRS change of $< \text{abs}(1)$), 1 grade worse, 2 grades worse, 3 grades worse and 4 grades worse. The summary will be presented for all patients, patients with at least 6 months of treatment, patients with at least 9 months of treatment and patients who have completed the treatment period. Patients will be counted in each treatment duration category whose criteria they have met (i.e. A patient who has completed the treatment period will be included in the denominator for all patients, patients with at least 6 months of treatment, patients with at least 9 months of treatment and patients who have completed the treatment period.).

All VRS data will be presented in a data listing for the safety population.

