4.1. General Methodology

Continuous data will be described using descriptive statistics including patient count (n), mean, standard deviation (SD), median, minimum, and maximum. Categorical data will be described using the patient count and percentage in each category. The percentage will be suppressed when the count is zero for a category in order to draw attention to the non-zero counts. Where specified on the table shells, a row denoted "Missing" is to be included in count tabulations to account for dropouts and missing values. The denominator for all percentages will be the number of patients in that treatment arm within the analysis population of interest, unless otherwise specified.

Patients will be identified in the listings by the patient identification number concatenated with the investigator/site number. Data will be displayed in all listings sorted by patient identification number concatenated with the investigator/site number. Data listings, unless otherwise specified, will include all patients who provide consent to participate in the study.

Unscheduled results will not be included in the summary tables except for determining Baseline values for efficacy and safety evaluations and the handling of laboratory data both at Baseline and during treatment (see Section 4.2). For patients discontinuing from the study, planned study visit data that are collected at the early termination visit will be included in by-visit summaries in the summary tables or figures (e.g. PRO questionnaires) using the serial next visit number associated with what would have been the patient's next scheduled visit. Thus, for example, a patient discontinuing from the study after Treatment Visit 2 would have efficacy and safety data obtained at the study termination visit treated as Treatment Visit 3 results. Data listings will include all data from scheduled, repeated, unscheduled and early termination visits.

All p-values will be rounded to three decimal places. If a p-value is less than 0.001 it will be reported as "<0.001." If a p-value is greater than 0.999 it will be reported as ">0.999." Point estimates of the parameter of interest will be generated along with, where appropriate, 95% confidence intervals.

All analyses will be conducted using SAS Version 9.2 or higher.

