4.2. Baseline, Study Day and Analysis Visit Windows

Unless otherwise specified, "Baseline" for efficacy and safety information is defined as the last non-missing evaluation taken prior to the first dose of study medication during the TR03 extension study (including repeated and unscheduled assessments).

For variables that require the analysis of change from baseline, the post-baseline assessment value minus the baseline assessment value will be used to derive change from baseline value. If either value is missing then the change from baseline will also be missing.

When study day is used for display or in comparisons, the following algorithm will be used:

- Study day = date of assessment – date of first dose of study medication + 1, if the date of the assessment is on or after the date of first dose;
- Study day = date of assessment – date of first dose of study medication, if the date of the assessment is prior to the date of first dose.

No analysis visit windows will be defined for this study, i.e., by-visit assessments will be based on the designated scheduled visit number associated with the data recorded for the endpoint of interest.

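### SAP Section 8.1.3 gives the VRS a 0-to-5 range, but its nine change categories fit only a five-level scale, so one of the two statements is wrong

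*SAP*

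**What the plan says.** Section 8.1.3 describes the VRS as three sensations (itchy, burning, stinging) and codes each one "from 0 = none; to 5 = very severe". It first sends each sensation to the general summaries of Section 8.1. It then adds a categorical table, in which "change between baseline and LOV will be summarized using frequencies and percentages for the following categories". The improvement side runs "4 grades better, 3 grades better, 2 grades better, 1 grade better". A no-change category follows, defined as an absolute change below 1. The worsening side runs "1 grade worse, 2 grades worse, 3 grades worse and 4 grades worse". The list has no open-ended end category and no residual category.

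The table is produced for each sensation in four groups: all patients, those with at least 6 months of treatment, those with at least 9 months, and those who completed the treatment period. Section 4.2 defines change in the usual way: "the post-baseline assessment value minus the baseline assessment value will be used to derive change from baseline value". Section 4.1 provides a Missing row where the table shells call for one, to account for dropouts and missing values.

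**The concern.** A categorical change table should have a row for every change that its scale allows. On a scale from 0 to 5 the largest possible change is 5 grades in either direction, but the list stops at 4. The two statements stand a few lines apart in one section and do not agree.

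If the range is right, the list has no place for the best possible response, from very severe to none, or for its mirror image. A programmer who met such a value would have to leave the patient out of the rows or merge the patient into a 4-grade category, and the SAP authorises neither. If the list is right, the stated range is wrong, and the SAP misdescribes the scale of a named secondary endpoint. Section 1 gives the SAP precedence over the protocol where the two differ on statistical analysis, so the SAP text itself should be correct.

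**Working it through.** **Inputs, all from the SAP**
- Stated range: 0 to 5 (Section 8.1.3).
- Categories: 4 better, 1 no change, 4 worse (Section 8.1.3).
- Change = LOV score minus baseline score (Sections 4.2 and 8.1.3).
- Assumption: scores are whole numbers. The graded adjectives and the grade-by-grade categories imply this. The no-change category then means a change of exactly 0.

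**The plan's own list.** 4 + 1 + 4 = 9 categories, covering changes from −4 to +4.

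**What a scale of k levels needs.** Changes run from −(k − 1) to +(k − 1), so there are 2k − 1 distinct values. There are k² possible pairs of baseline and LOV scores. For d ≥ 1, a change of size d arises from 2(k − d) pairs.

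| Scale | Levels k | Pairs k² | Distinct changes 2k − 1 | Pairs covered by the nine categories | Pairs not covered |
|---|---|---|---|---|---|
| 0 to 5 (as stated) | 6 | 36 | 11 (−5 to +5) | 34 | 2 |
| 0 to 4 | 5 | 25 | 9 (−4 to +4) | 25 | 0 |
| 1 to 5 | 5 | 25 | 9 (−4 to +4) | 25 | 0 |

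For the stated scale, the covered pairs are 6 with no change plus 2 × (5 + 4 + 3 + 2) = 28 with a change of 1 to 4 grades, which makes 34. The remaining 2 × (6 − 5) = 2 pairs are 5 to 0 and 0 to 5. For five levels, the sum is 5 + 2 × (4 + 3 + 2 + 1) = 25, so every pair has a row.

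These are counts of possible score pairs. They are not an estimate of how many patients would be affected.

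**Does anything else in the SAP supply the missing rows?**
- The Missing row in Section 4.1 is for dropouts and missing values. An observed change of 5 grades is neither.
- No other section gives a different VRS range or a rule for a 5-grade change.
- Other category lists in the SAP end in an open category: ItchyQoL worsening above 50% (Section 8.1.5), more than 100 lesions on the PAS (Section 8.1.8), and a SOWS total above 60 (Section 9.2.1). The VRS list does not.

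**Size of the effect if the scale is 0 to 5.** If m of N patients in a group make a full-range change in one sensation, the nine rows together fall short by 100 × m/N percentage points. The layout has 3 sensations × 4 duration groups = 12 such distributions. Neither m nor N can be taken from the SAP, and Section 4.3 says that the sample size cannot be predicted. If m = 0, the shortfall is zero.

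**The case against.** The strongest reply is that the nine categories fit a five-level scale exactly. The 5 in the range may therefore be the slip, in which case no patient is left without a row and only one figure in the text needs correcting. This stands as a possibility, but the SAP cannot settle it, and the mismatch remains under either reading.

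A reader might also infer that patients with the most extreme changes are lost from the VRS endpoint. The SAP does not support that. The grade-change table is an addition to the Section 8.1 summaries, which give values and changes at each treatment visit, at the washout visit and at LOV. A change of 5 grades in either direction enters those means, SDs, minima and maxima without difficulty, and all VRS data are listed. The secondary endpoint in Section 3.3.2 does not require the grade-change table.

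Nor do the documents support saying flatly that the percentages will not add to 100%. For this cause, that needs both a 0-to-5 scale and at least one full-range change. Rows can also fall short for another reason: Section 4.1 takes the analysis population as the default denominator and includes a Missing row only where the shells specify one.

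Finally, the two directions are not equally likely. Treatment entry requires a Worst Itch NRS of at least 5 (Section 3.1), so a baseline itch VRS of 0 is improbable. Burning and stinging have no such threshold, and an improvement from 5 to 0 is not ruled out for any sensation. This makes a large count unlikely but does not close the gap in the list.

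**Conclusion.** The inconsistency is certain, given whole-number scoring: a 0-to-5 range needs 11 change categories, the SAP lists nine, and nine fit a five-level scale. The consequence is conditional. Only if the scale really is 0 to 5, and only if some patient makes a full-range change between baseline and LOV, does the supplementary table omit that patient and fall short of its denominator.

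Severity is minor. The study is open-label, all patients are summarised in a single nalbuphine group, and no inferential statistics are planned. The primary endpoint is TEAEs, and no estimate, test or decision depends on this table. Few or no patients are likely to be affected, though that is a judgement and the SAP gives no figure for it.

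**What to change.** Check the VRS response options on the instrument or the eCRF, then make the two statements in Section 8.1.3 agree:
- If the scale is 0 to 5, add the categories 5 grades better and 5 grades worse to the text and the table shell.
- If the scale has five levels, correct the stated range and keep the nine categories.

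The cost is one line of SAP text and at most two rows in the table shell. It is best done before the table is programmed. No other analysis changes.

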3.1. Overall Study Design and Plan

This is an open label safety and tolerability extension study for patients who have completed the TR03 study. Patients will either enter directly into a drug Treatment Period (Worst Itch NRS ≥ 5) or enter an extended screening period of a no-drug Observation Period (Worst Itch NRS < 5) based on their reported NRS scores on the first Visit (Visit 1a). For up to 12 extended screening weeks, patients in the no-drug Observation Period may also transition into the drug Treatment Period if their Worst Itch NRS increases to ≥ 5 .

To allow for various starting levels of pruritus intensity, patients who have a Worst Itch NRS that is ≥ 5 will enter the Treatment Period upon completion of Visit 1a. Patients whose Worst Itch NRS score is < 5 will be entered into an extended screening period, no-treatment criteria Observation Period for up to 12 weeks or until they develop a higher level of pruritus (i.e., Worst Itch NRS ≥ 5), at which point they will transition to the Treatment Period upon completion of Visit 1b. All patients entering the Treatment Period, whether immediately upon study entry or following a period of time in the Observation Period, will initially be titrated to a dose that can be as high as 180 mg twice daily (BID) during the first 4 weeks of the Treatment Period. Patients who continue in the Observation Period and maintain a Worst Itch NRS score of < 5 will be screen failed from the study at the end of the 12-week period. For enrolled patients whose Visit 1a worst itch NRS score satisfies the ≥ 5 enrollment criterion and for whom treatment is initiated, the screening visit Visit 1a will also be designated as the baseline visit. For enrolled patients who must continue into the Observation Period, the first visit during that period when the worst itch NRS ≥ 5 criterion is satisfied will be designated as Visit 1b and that visit will serve as the baseline visit.

The total study duration for any individual patient will be up to 53 weeks. For patients who enter directly into the Treatment Period, the total amount of time on drug will not exceed 50 weeks. Patients who enter the Treatment Period from the Observation Period, the total amount of time spent in the combined two periods of the study cannot exceed 50 weeks. All patients who received drug treatment will have a 2-week Washout and Safety Follow-up period at the end of the dosing period, unless consent is withdrawn.

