The total amount of time in the Observation Period cannot exceed 12 weeks. After these 12 extended screening weeks, patients not eligible for the Treatment Period are screen failed from the study. The study periods are summarized below.

Study Period	Study Weeks	Duration
Observation Period	
Patients who do not meet the criteria to start Treatment are followed in Observation Period visits (OV) for up to 12 extended screening weeks. During this time, the patient may meet criteria and become eligible to enter the Treatment Period. If the patient does not meet the criteria to enter the Treatment Period by the end of 12 extended screening weeks (OV12), participation in the study ends and the patient is screen failed
	Up to 12 Extended Screening weeks
Treatment Period	
For patients directly entering the Treatment Period as of Visit 1a, the Treatment Period begins with Study Week 1 (Visit 1a) and ends with Study Week 50.
 
For patients entering the Treatment Period after being followed in the Observation Period, the number of weeks on treatment and the end of the Treatment Period varies. (See Table 8 in the study protocol for the details of which treatment visits are to take place).
 
The End of Treatment Visit will take place after the patient completes the last week of study drug.
	Up to 50 weeks
Washout and Safety Follow-Up Period	
The Washout and Safety Follow-up Period is two (2) weeks in duration.
 
For patients directly entering the Treatment Period as of Visit 1a and completing 50 weeks of study drug treatment, the Washout and Safety Follow-up Period should take place during weeks 51 and 52.
 
For patients entering the Treatment Period after being followed in the Observation Period, the number of weeks on treatment and the end of the Treatment Period varies; Table 8 in the Study Protocol calculates the Treatment Visit assignments for any patient entering the Treatment Period from the respective Observation Period visits. The Washout and Safety Follow-up Period will take place during the two (2) weeks after the patient completes the last week of study drug.
 
The Washout and Safety Follow-up Period Visit will take place in the week following the completion of the two (2) week Washout and Safety Follow-up Period.
	2 weeks

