3.2.2. Premature Discontinuation of Study Drug Treatment For Reasons Other Than Failure-to-Improve

Patients who complete Study Drug treatment through the End of Treatment Visit 14 (TV14) (even if some doses have been missed or if the patient was followed in the Observation Period before receiving study drug treatment) are considered to have completed Study Drug treatment. Patients discontinuing Study Drug treatment prior to the maximum allowable number of Treatment Weeks (based on their entry into the study at either Visit 1a or Visit 1b) will also be considered to have prematurely discontinued Study Drug treatment. Patients discontinuing Study Drug treatment prior to End of Treatment Visit 14 will be considered to have prematurely discontinued Study Drug treatment and will be asked to complete the End of Treatment Visit (TV14) regardless of where they were in the study visit schedule, the Washout and Safety Follow-up Period Visit and the Premature Discontinuation of Study Drug Telephone Contact visit. Patients removed from the study after enrollment and who have received a dose of study drug will not be replaced.

Some reasons for premature discontinuation of Study Drug treatment include:

- Intercurrent illness
- Any intolerable Adverse Event (AE) that cannot be ameliorated or safely managed with medical intervention or one that poses undue risk to the subject if Study Drug treatment were continued in the opinion of the Medical Monitor or Investigator
- Electrocardiogram (ECG) changes summarized in protocol Section 17.4
- Opioid medication is introduced in anticipation for chronic use of greater than 2 weeks
- Any medication prescribed for chronic anti-pruritic use of greater than 2 weeks
- Development of substance abuse as determined by the Investigator.

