8.1.5. Change from Baseline in the ItchyQoL

The ItchyQoL consists of 22 pruritus-specific items measuring how pruritus affects patients' QOL in the area of symptoms related to the itch condition (6 questions), functional limitations (7

questions), and emotions (9 questions). The subject scores each question never =1, rarely=2, sometimes=3, often=4 and all the time=5.

Individual scores for each of the 22 items will be summarized categorically using frequencies and percentages at each study visit.

The ItchyQoL total score will be obtained as the sum of the 22 items. If no more than three items are missing, each missing item will be estimated as the mean of the remaining items. If more than three items are missing, the ItchyQoL total score will be set to missing.

Summaries for ItchyQoL total score will be presented as detailed in Section [8.1](#). In addition, change in ItchyQoL total score between baseline and LOV will be summarized using frequencies and percentages for the following categories: very good improvement, marked improvement, some improvement, no change, slightly worse, markedly worse and much worse. The magnitude of ItchyQoL change associated with each category is taken from [Siebenhaar et al., 2013](#): Very good improvement: > 50% to 100% reduction; Marked improvement: > 20% to 50% reduction; Some improvement: > 5% to 20% reduction; No change: 5% reduction to 5% increase; Slightly worse: > 5% to 20% increase; Markedly worse: > 20% to 50% increase; Much worse: > 50% increase. The summary will be presented for all patients, patients with at least 6 months of treatment, patients with at least 9 months of treatment and patients who have completed the treatment period. Patients will be counted in each treatment duration category whose criteria they have met (i.e. A patient who has completed the treatment period will be included in the denominator for all patients, patients with at least 6 months of treatment, patients with at least 9 months of treatment and patients who have completed the treatment period.).

Individual ItchyQoL item scores as well as the calculated total score for each patient will be presented in a data listing for the safety population.

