8.1.8. Change from Baseline in PAS

The PAS consists of 7 qualitative and quantitative measurements related to the examination of the skin. Type, number, distribution, affected body parts, and quantitative number of lesions in a representative body part are documented. The biggest lesion and the most representative lesion are monitored with documentation of height and area measurements. Prurigo lesion activity is recorded as a percentage based on their stage (0-4).

Separate activity classification is provided for prurigo lesions with excoriations/crusts compared to all prurigo lesions and for healed prurigo lesions compared to all prurigo lesions. The proportion of patients with each stage of classification will be summarized at each visit for each of the two activity classifications (note that PAS is not completed at the Washout/Safety and Follow-up visit). Shift from baseline to LOV and the End of Treatment visit for all patients, patients with at least 6 months of treatment, patients with at least 9 months of treatment and patients who complete treatment will also be presented for each of the two activity classifications. Shift from baseline to Visit 5/Week 13, Visit 8/Week 26 and Visit 11/Week 38 for all patients will also be presented for each of the two activity classifications.

Classification is provided for total number of prurigo lesions (not including scars). The proportion of patients at each classification level (0, 1-19, 20-100 and >100) will be summarized at each visit (note that PAS is not completed at the Washout/Safety and Follow-up visit). Shift from baseline to LOV and the End of Treatment visit for all patients, patients with at least 6

months of treatment, patients with at least 9 months of treatment and patients who complete treatment will also be presented. Shift from baseline to Visit 5/Week 13, Visit 8/Week 26 and Visit 11/Week 38 for all patients will also be summarized.

All PAS data obtained in the study will be presented in a data listing for the safety population

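### Sections 8.1.3 and 8.1.5 place every treatment completer in the 9-month denominator, although a completer who entered after 12 observation weeks has at most 38 weeks of treatment

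*SAP*

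**What the plan says.** Section 8.1.3 (VRS) and Section 8.1.5 (ItchyQoL) each summarise change from baseline to the last observed value in four overlapping groups: all patients, those treated for 6 months or more, those treated for 9 months or more, and treatment completers. In both sections the general rule counts a patient in every group whose criterion the patient satisfies. A parenthetical introduced by 'i.e.' follows: in Section 8.1.3 a completer is "included in the denominator for all patients, patients with at least 6 months of treatment, patients with at least 9 months of treatment and patients" finishing treatment. Section 8.1.5 has the same parenthetical and the same groups ("patients with at least 9 months of treatment and patients who have completed the treatment period"). Neither makes an exception for late entry.

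Section 8.1.8 (PAS) uses the groups as well ("patients with at least 9 months of treatment and patients who complete treatment"), but has no statement placing completers in all of them.

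On treatment length, Section 3.1 says that for patients entering from the Observation Period "the total amount of time spent in the combined two periods of the study cannot exceed 50 weeks". It also says "The total amount of time in the Observation Period cannot exceed 12 weeks", and that for these patients "the number of weeks on treatment and the end of the Treatment Period varies". Section 3.2.2 treats a patient who reaches the End of Treatment Visit (TV14) as a completer, "even if some doses have been missed or if the patient was followed in the Observation Period before receiving study drug treatment".

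**The concern.** The parenthetical holds only if completing treatment implies at least 9 months on drug. That is so for a direct entrant with 50 weeks. It is not assured for a patient who used most of the observation allowance, because each observation week comes off the longest possible treatment period.

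At stake is whether the 9-month denominator matches its label and can be reproduced. A programmer who follows the general rule, using exposure days, would leave out a completer with 38 weeks under a calendar-month or 30-day-month threshold. A programmer who follows the parenthetical would include that patient. Both could point to the SAP.

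**Working it through.** There is no stated figure to reproduce, so the check is direct arithmetic.

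**Inputs from the SAP**
- Cap on observation plus treatment: 50 weeks (Section 3.1).
- Longest observation: 12 weeks (Section 3.1). Entry remains possible up to that limit, since only a patient who "does not meet the criteria to enter the Treatment Period by the end of 12 extended screening weeks (OV12), participation in the study ends".
- Completer status: includes patients who came through the Observation Period (Section 3.2.2).
- Exposure: last dose date minus first dose date plus 1, in days (Section 7.3.2).

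**Assumption.** The SAP does not say how long a month is, so three conventions are compared:
- Calendar months: nine span 273 to 276 days depending on the start date; the mean is 9 x 30.4375 = 273.9 days.
- 30-day months: 9 x 30 = 270 days.
- 28-day months: 9 x 28 = 252 days.

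**Formula.** With w weeks in observation, the longest treatment is (50 - w) x 7 days.

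| Observation weeks w | Longest treatment | Mean calendar months (days / 30.4375) | Against 273 to 276 days | Against 270 days | Against 252 days |
|---|---|---|---|---|---|
| 0 | 50 weeks = 350 days | 11.50 | met | met | met |
| 10 | 40 weeks = 280 days | 9.20 | 4 to 7 days over | 10 over | 28 over |
| 11 | 39 weeks = 273 days | 8.97 | 0 to 3 days short | 3 over | 21 over |
| 12 | 38 weeks = 266 days | 8.74 | 7 to 10 days short | 4 short | 14 over |

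**Break-even.** Nine mean calendar months are 273.9 / 7 = 39.1 weeks, which leaves room for 50 - 39.1 = 10.9 observation weeks. Nine 30-day months are 270 / 7 = 38.6 weeks, which leaves 50 - 38.6 = 11.4. A patient who enters later than that cannot reach 9 months, yet can be a completer.

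**The 6-month category.** Six mean calendar months are 6 x 30.4375 = 182.6 days. Even the shortest full course, 266 days, exceeds this, so the parenthetical is right for that column.

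**The case against.** The strongest reply is that the general rule governs. It already admits patients by criterion, and the parenthetical only illustrates that the groups overlap. This stands in part: the rule would exclude a 38-week completer under calendar or 30-day months, so the fault lies in the parenthetical and not in the tables' basic design. But the parenthetical is worded as an explanation of the rule, without exception, so the two statements still give different denominators.

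The second reply is that the month is undefined. With 28-day months, or with the Week 38 visit as the 9-month mark, a 38-week completer qualifies. Section 8.1.8 does present PAS shifts at Weeks 13, 26 and 38, which makes the latter plausible. The SAP does not label Week 38 that way and states no 28-day convention, so the conflict vanishes only under a reading that it does not give.

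Several stronger readings are tempting, but the SAP does not support them:
- A reader might infer that entrants after 11 weeks are also misclassified. At 273 days they can have nine full calendar months, and they exceed 270 days.
- A reader might infer that the PAS tables carry the same contradiction. Section 8.1.8 shares the columns but not the completer statement.
- A reader might take these columns to be the only view of response by time on treatment. Section 8.1 gives summaries at every treatment visit, and Section 8.1.8 gives PAS by visit and at three fixed weeks.
- A reader might count the spread among completers, 266 to 350 days or (350 - 266) / 350 = 24%, as an error. Sections 3.1 and 3.2.2 disclose that treatment length varies and that observation entrants count as completers.
- A reader might conclude that late entrants have no treatment visits past about Week 38. Visit assignment follows Table 8 of the protocol, which is not at hand.

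**Conclusion.** The point holds in a narrow form. In Sections 8.1.3 and 8.1.5 the parenthetical contradicts both the rule it explains and the label of the 9-month column for completers who entered after about 12 observation weeks. Their shortfall is 4 days under 30-day months and 7 to 10 days under calendar months.

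This rests on two assumptions: that a month is a calendar month or 30 days, and that a patient can spend the full 12 weeks in observation before the first dose. The 38-week ceiling for such a patient follows from the cap in Section 3.1, whatever visits the protocol's Table 8 assigns.

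The consequence is minor. The tables are descriptive and no testing is planned. The number of patients who both entered this late and completed is not given and may be zero.

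**What to change.** - **Sections 8.1.3, 8.1.5 and 8.1.8:** define the 6- and 9-month categories in days of exposure as derived in Section 7.3.2. Cut-offs of at least 183 and at least 274 days would match mean calendar months (182.6 and 273.9 rounded up). Another stated cut-off would serve, but the choice decides the borderline case: 273 days fails 274 and passes 270.
- **Sections 8.1.3 and 8.1.5:** make the parenthetical conditional, so that a completer is counted in the 6- and 9-month groups only if the exposure threshold is met.
- **Section 8.1.8:** nothing beyond the day-based definition is needed.
- **Optional:** footnote the completer column with the possible exposure range for a full course, 38 to 50 weeks.

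The cost is a sentence or so per section and a derivation from dates already collected. The downside is that the 9-month column may lose a few patients, and completers are no longer strictly nested within it.
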